-	Study Week		Week 0	Week 1	Week 2	Week 3	Week 4	Week 5	Week 6 or ET at week 6	Week 7	Week 8	Week 9	Week 10	Week 11	Week 12	Any visit other than at week 6
Medical His	tory	X														
Physical Ex	am	Х														
MINI		Х														
Pregnancy Test (Females only)		X														
Post-Screer Pregnancy Checklist	ning		X			Х			X			Х				
ECG		Х							Х						Х	Х
Labs (CMP, Panel, CBC CRP, IL6, T	, Hs- NFα)	X							X						Х	X (only CMP, Lipid panel, and CBC)
Lab (HbA10	C) ⁴	Х														
Vital Signs		X	Х	Х	Х	Х	Х	Х	Х	Х	Х	Х	Х	Х	Х	Х
Height		X	Х													
Weight		X	Х	Х	Х	Х	Х	Х	Х	Х	Х	Х	Х	Х	Х	Х
Waist Circumferer	nce		Х						Х						Х	
TLFB ¹		Х	Х	Х	Х	Х	Х	Х	Х	Х	Х	Х	Х	Х	Х	Х

VAS	Х	Х	Х	Х	Х	Х	Х	Х	Х	Х	Х	Х	Х	Х	Х
Urine Drug Screen	Х	Х	Х	Х	Х	Х	Х	Х	Х	Х	Х	Х	Х	Х	Х
Fagerstrom Test	Х							Х						Х	
Adverse Events		Х	Х	Х	Х	Х	Х	Х	Х	Х	Х	Х	Х	Х	Х
PANSS		Х						Х						Х	
SANS		Х						Х						Х	
CDRS		Х						Х						Х	
CGI-S and CGI-I ²		Х						Х						Х	
CSSRS	Х	Х						Х						Х	Х
QOL		Х						Х						Х	
EPS Scales (BAS, SAS, AIMS)		Х						Х						Х	
Drug dispensing		Х	Х	Х		Х		Х		Х		Х			
Supportive Counseling		Х	Х	Х	Х	Х	Х	Х	Х	Х	Х	Х	Х	Х	

1- TLFB at screening will be completed for the past 30 days. All other visits the TLFB will collect information for the past week.

2- CGI-I will not be administered at baseline. Only CGI-S is administered at baseline.

- 3- EOT end of treatment
- 4- Lab (HbA1C) will only be performed at the screening visit

5- If ET falls on week 6, the visit should follow regular week 6 protocol. If ET falls on any other visit, follow ET protocol

Informed Consent Process: All subjects will sign IRB approved informed consent form (ICF) prior to starting any study related screening procedures. The written informed consent will be obtained by authorized study personnel. The authorized study staff will explain the study objectives, risks and benefits and overview of the study procedures to all subjects as part of the consent process.

Eligibility Review: An eligibility review will be conducted by the investigator at each site as per the inclusion exclusion criteria listed in section D of the protocol. All subject eligibility criteria will be reviewed by UMass designee prior to subject randomization.

Demographics and Medical/Psychiatric History: Subject's demographics, medical and psychiatric history will be collected as part of the screening process. All patient medical and psychiatric history will be reviewed by the investigator.

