Any clinically significant change noted from screening or if an ECG is considered abnormal and clinically significant, it will be reported as an AE and will be appropriately recorded in both the source documents and the eCRF.

Laboratory Procedures: Most of the lab procedures will be done at the site. All blood work will be done as fasting.

Routine lab panels done at site include: Hematology (CBC with diff), comprehensive metabolic panel (CMP) and lipid panel. These labs will be assessed at screening, week 6 and week 12. Routine lab panels will be collected for subjects who are early terminated. Additionally, an HbA1c test will be conducted at screening only. Approximately four tablespoons of blood will be taken at each blood draw.

Lab samples for Hs-CRP, IL6 and TNF -alpha will be collected by sites and stored at -80F. It will be batch shipped to UMass every 6 months. These will be analyzed at UMass Memorial labs. CRP, IL-6 and TNF- α are well established inflammatory markers that are associated with both psychopathology and metabolic side effects in patients with schizophrenia. We will analyze how brexpiprazole treatment might affect these inflammatory markers.

Hematology (CBC)	Comprehensive metabolic panel	Lipid Panel
Hematocrit	Alanine transferase	Total cholesterol
Hemoglobin	(ALT)	Chol, HDL
Platelets	Albumin	Triglyceride
	Total protein	Chol, LDL

Routine Lab Assessments at site:

Red blood cell	Alkaline	Chol, VLDL
count	phosphatase (ALK-	Cholesterol/DL ratio
Total and	P)	
differential	Aspartate	
(absolute) white	transferase (AST)	
blood cell count	Bicarbonate	
	Blood urea nitrogen	
	(BUN)	
	Creatinine	
	Glucose	
	Potassium	
	Sodium	
	Chloride	
	Estimated	
	glomerular	
	glomerular filtration	
	rate (eGFR)	

Future Testing: Blood samples will be collected at screening, week 6 and week 12 for use in future research related to schizophrenia. All samples will be labelled with a study ID. Only members of the research team will be able to derive an individual's identity from their study ID code. The key to the code is stored on secure server and can only be accessed through password-protected computer Sub-sites will store these at -80F and batch ship them to the UMass Psychotic Disorders Research Program at UMass Medical School for storage and future extraction/genotyping. The lead site will store all samples indefinitely.

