"No desire at all" (marked with a "0") and on the left side with "Worst imaginable desire" (marked with a "100" with a line connecting the two ends. Subjects will mark the appropriate point to indicate where their "desire for substance" falls on this line.

Fagerstrom Test: The Fagerstrom Test for Nicotine Dependence will be used to assess smoking status. Data on subjects will be collected using the Fagerstrom test as per the schedule of events.

Positive and Negative Syndrome Scale (PANSS): PANSS is a measure used to assess symptom severity in patients with schizophrenia. It consists of three sections: Positive scale has 7 items, Negative scale has 7 items and General

Psychopathology has 16 items. Each item (symptom) will be scored on a 7-point scale with higher scores representing increasing levels of psychopathology: 1) Absent, 2) Minimal, 3) Mild, 4) Moderate, 5) Moderate severe, 6) Severe, and 7) Extreme. The PANSS will be administered by a designated study staff at time points specified in the schedule of events.

Schedule of Assessment of Negative Symptoms (SANS): SANS is a 24-item scale used to assess negative symptoms based on observation and a structured interview in patients with schizophrenia. Designated study staff will administer the SANS at baseline, week 6 and week 12.

Calgary Depression Rating Scale (CDRS): The Calgary Depression Rating Scale is used to depression symptoms in subjects. The PI or a designated staff will administer the CDRS at baseline, week 6 and week 12.

Clinical Global Impression – Severity and Clinical Global Impressions – Improvement Scales (CGI-S and CGI-I): The CGI-S and CGI-I are observer rated scales. The CGI-S measures illness severity on a 7-point Likert scale 1) Normal, not at all ill, 2) Borderline mentally ill, 3) Mildly ill, 4) Moderately ill, 5) Markedly ill, 6) Severely ill, and 7) Among the most extremely ill patient. The CGI-I is used to measure improvement in illness and also uses a 7 point Likert scale: 1) Very much improved, 2) Much improved, 3) Minimally improved, 4) No change 5) Minimally worse, 6) Much worse, 7) Very much worse. The PI or a designated study staff will administer this at time points as per the schedule of events.

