Study intervention: Brexpiprazole switch: For the brexpiprazole group, an overlap and taper switch method will be used. The current antipsychotic medication will be tapered following standard clinical practice and discontinued over a time period of 6 weeks. Brexpiprazole will be started at 1mg/day for 4 days, and 2mg/day for 3 days, and then titrate by up to 1mg/day increase every 3 days to reach 4mg/day, or as much and as fast as the participant can tolerate. Participants will stay on 4mg/day or the highest tolerable dose until the end of the study.

Medication adherence will be measured via pill counts at weekly visits. The study staff will discuss pill count data with participants to emphasize the need to take the study medication.

If participants cannot tolerate brexpiprazole after randomization, it will be stopped, though the participant may continue to be followed on another treatment (ideally their pre-study antipsychotic medication) for the remaining weeks of the study. The subject will then continue the rest of the study on their previous antipsychotic medication.

The following assessments will be completed at baseline visit:

- 1) Anthropometric measures (weight, waist circumference and height at screening to be used) and Vital signs
- 2) Weekly TLFB
- 3) Drug screen
- 4) Post-Screening Pregnancy Checklist
- 5) AE review
- 6) PANSS, SANS, QLS, CGI-S
- 7) C-SSRS, EPS scales, CDRS
- 8) Supportive counseling

Week 6 and week 12 visits: The following assessments will be done at week 6 and 12.

- 1) Anthropometric measures (weight, waist circumference) and Vital signs
- 2) Weekly TLFB
- 3) Drug screen
- 4) Post-Screening Pregnancy Checklist (Week 6 only)
- 5) AE review
- 6) PANSS, SANS, QLS, CGI-S
- 7) C-SSRS, EPS scales, CDRS
- 8) Supportive counseling
- 9) ECG
- 10)Labs (CMP, CBC, lipid panel)
- 11)Labs hs-CRP, IL-6 and TNF-alpha collected and stored at -80F
- 12)Fagerstrom test

Week 2, 3,4,5,7,8,9,10,11 visits: These visits may be completed virtually through a secured platform depending on the most current COVID situation. During the virtual routine follow up visits, vital signs and urine drug screen will be unable to be collected; but all subjects who go through the switch will have demonstrated no clinically significant changes in vitals, ECG, or lab results in prior long visits. The following assessments will be administered at these weekly visits:

- 1) Vital signs and anthropometric measures (weight)
- 2) Urine drug screen

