- 3) Post-Screening Pregnancy Checklist (Week 3 and 9 only)
- 4) TLFB
- 5) AE review
- 6) Supportive counseling

End of Study / Discontinuation of Study Medication – When a participant who is randomized to brexpiprazole completes Visit 12 (or sooner for those discontinuing study medication), he or she will no longer receive medications through the study. There will need to be a discussion with the participant and his/her treatment provider as to whether or not the participant will continue on the study medication after the subject's study participation is over. For participants finishing the study at Visit 12, this discussion should occur about three weeks prior to the final visit. If the participant will continue on the study medication study medications following standard clinical practice. The monitoring and management of symptoms, therapeutic response and medication side effects will be the responsibility of the treatment provider.

Subjects who do not wish to continue on the study medication after the end of study, the treatment provider can begin to manage a cross titration off the study medication and on to either the antipsychotic medication prior to the study or a new antipsychotic medication following standard clinical practice. The monitoring and management of symptoms, therapeutic response and medication side effects will be the responsibility of the treatment provider.

Withdrawal of Subjects

Subjects are free to discontinue their participation in the study at any time and without prejudice to further treatment. The investigator must withdraw any subject from the study who requests to be withdrawn or fits the criteria below:

- 1) If subject meet any exclusion criteria after enrollment.
- 2) If subjects have laboratory results that meet the exclusionary criteria range during the study, the subject will have his/her labs repeated before being withdrawn from the study.
- 3) Subjects will be withdrawn from the study is there is an increase in their PANSS total score greater than or equal to 20 compared to their baseline total score at any point during the study.
- 4) Female subjects may be terminated from the study if they become pregnant at any time while participating in the study.
- 5) If at any time the study sponsor or research personnel at UMass decide to terminate the study, subjects' consent will be withdrawn involuntarily.

Early Termination Visit

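### The virtual-visit safety premise cannot hold for ECG and labs at weeks 2–5, the rules on intolerance conflict, and leaving the study before week 6 yields no post-baseline symptom or quality-of-life rating

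*Combined protocol and SAP*

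**What the plan says.** **Virtual visits.** Section F allows the visits at weeks 2, 3, 4, 5, 7, 8, 9, 10 and 11 to be virtual, depending on the COVID situation. It accepts that at such visits "vital signs and urine drug screen will be unable to be collected" and gives as its reason that "all subjects who go through the switch will have demonstrated no clinically significant changes in vitals, ECG, or lab results in prior long visits". For the routine panels, Section E (Laboratory Procedures) states: "These labs will be assessed at screening, week 6 and week 12", with a further set for early terminators. Table 1 places the ECG at the same time points. Vital signs are marked at every visit, and week 1 is not on the virtual list.

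**The switch.** Under Section F (Study intervention), the previous antipsychotic is tapered and "discontinued over a time period of 6 weeks". Brexpiprazole is given at 1 mg/day for 4 days, followed by "2mg/day for 3 days, and then titrate by up to 1mg/day increase every 3 days to reach 4mg/day", subject to tolerability.

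**Intolerance.** The same part of Section F says that brexpiprazole is stopped in participants who cannot tolerate it, and that they may be followed on another treatment for the remaining weeks. Section G (Study Drug Dose and Administration) allows dose reduction, but says that anyone unable to tolerate at least 1 mg is withdrawn from the study.

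**Symptom ratings.** On the PANSS, Section E says: "The PANSS will be administered by a designated study staff at time points specified in the schedule of events". Table 1 shows it at baseline, week 6 and week 12, as it does SANS, CDRS, CGI and QOL. An exit at week 6 gets the full week 6 battery; otherwise, footnote 5 says: "If ET falls on any other visit, follow ET protocol". The Section F list for that visit has seven safety items and none of these scales, and their cells in the Table 1 early-termination column are blank. Section F's withdrawal criteria include the following: "increase in their PANSS total score greater than or equal to 20 compared to their baseline total score at any point during the study".

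**Analysis.** Section L plans an intent-to-treat mixed model for psychiatric symptoms and quality of life over all 12 weeks, including the switchover phase, with baseline values as covariates.

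**The concern.** Weeks 2–5 lie inside the six-week taper. The protocol does without in-person checks there on the strength of ECG and lab results that its own schedule does not produce until week 6. A site or ethics committee reading the sentence would believe that a safeguard is in place when it is not.

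The other two parts concern data. Section L intends the symptom model to cover the switchover phase, yet a participant who leaves the study during that phase gives it no outcome value. Some of these exits may be related to symptoms: withdrawal applies to anyone who comes to meet an exclusion criterion, and psychiatric instability is one. The intolerance route out exists only in the switch arm. Sections F and G disagree on whether such participants stay to the week 6 ratings, so the loss could differ between arms.

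**Working it through.** **1. ECG and labs before each virtual-eligible visit** (Table 1; Section E; Section F).

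| Virtual-eligible visits | Number | Earlier scheduled ECG and labs after the switch begins |
|---|---|---|
| Weeks 2, 3, 4, 5 | 4 | none (screening only) |
| Weeks 7, 8, 9, 10, 11 | 5 | week 6 |

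The total is 4 + 5 = 9 visits. At 4 of the 9, the only scheduled ECG and labs precede brexpiprazole, so absence of change cannot have been demonstrated.

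**2. Vital signs.** Week 1 is in person, so a post-switch reading exists before week 2. On the fastest written titration:
- 1 mg on days 1–4 and 2 mg on days 5–7;
- 3 mg from day 4 + 3 + 1 = 8;
- 4 mg from day 8 + 3 = 11.

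The week 1 reading (about day 7) therefore covers only the first week of the switch. Titration may be slower if tolerability requires.

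**3. Intolerance.** Because Section G allows dose reduction, participants who cannot tolerate brexpiprazole at all and those who cannot tolerate 1 mg can be the same people. Section F would let them continue to the week 6 and week 12 ratings. Section G would end their participation and, outside week 6, send them to the safety-only exit visit.

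**4. Expected leavers.** The plan's own figure is reproduced first: 40 / (1 − 0.20) = 50 randomized. Expected non-completers are 50 × 0.20 = 50 − 40 = 10. Participants who stop the drug but are followed to week 12 are not among these 10.

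**5. Leavers with no post-baseline symptom rating.** The documents do not give the timing of exits.
- Lower bound, all leave at week 6 or later: 0, so 50 of 50 have a post-baseline rating.
- Upper bound, all leave before week 6: 10, so 40 of 50 do.
- Even spread over 12 weeks (assumption): 10 × 5/12 = 4.2 to 10 × 6/12 = 5.0, which is 8.3% to 10% of 50.

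With baseline as a covariate, such a participant has no outcome record in the model. If baseline were also modelled as a response, that participant would still carry no information on change.

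**6. Precision.** At the upper bound, the standard error of a simple two-arm comparison rises by a factor of √(50/40) = 1.12. At 5 leavers the factor is √(50/45) = 1.05.

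**The case against.** Several stronger readings are tempting, and the documents do not support them.

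- *The whole premise is untrue in weeks 2–5.* Not for vital signs: the in-person week 1 visit means that part could be met, though only for the first week. If going through the switch means having completed it, the sentence is silent about weeks 2–5 rather than false. Those weeks then have no stated justification, so a gap remains on either reading.
- *Virtual visits lose ECG or lab data.* They do not, because none is scheduled at those visits. Virtual visits are also a contingency tied to COVID, so the nine visits are a maximum.
- *The PANSS withdrawal rule contradicts the schedule.* It applies throughout the study while ratings occur only at baseline, week 6 and week 12, but unscheduled ratings are not forbidden, and deterioration can also lead to withdrawal through the psychiatric-instability criterion. It is a secondary wording point.
- *The treatment comparison is biased, or the primary outcomes are compromised.* The documents do not show how many exits are symptom-related or how they split by arm. TLFB is collected weekly and at early termination, and Table 1 does the same for the craving VAS.

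It is also fair to say that safety oversight continues. Adverse events are reviewed at every visit, the investigator monitors continuously, a medical monitor reviews all events, and exit visits include ECG, labs and the C-SSRS. Restricting the exit visit to safety items is a deliberate choice that keeps it short. These arguments limit the seriousness of the point. They do not make the ECG and lab statement achievable, settle the disagreement on intolerance, or supply the missing ratings.

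**Conclusion.** The point holds in three limited parts. The virtual-visit premise cannot hold for ECG and labs at 4 of the 9 eligible visits; this follows directly from the schedule and needs no assumption. Sections F and G disagree on whether participants who cannot tolerate brexpiprazole remain in the study. Participants who leave in weeks 1–5 have no post-baseline PANSS, SANS, CDRS, CGI or QOL: 0 to 10 of 50, or about 4 to 5 if exits are spread evenly, on the plan's 20% discontinuation. Only secondary outcomes are affected in this way. The loss of precision is modest, at most a factor of 1.12 in a simple comparison. The reason to act is that the missing values may be informative and cannot be recovered later, not that a bias of known size or direction has been shown.

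**What to change.** 1. Reconcile the virtual-visit sentence and the list of virtual weeks in Section F with the ECG and lab time points in Table 1. The clinical content is for the sponsor's clinicians.
2. Reconcile Section F (Study intervention) with Section G (Study Drug Dose and Administration) on participants who cannot tolerate brexpiprazole, stating whether they remain in follow-up. Which rule applies is likewise for the clinicians.
3. Record the PANSS and, where feasible, SANS, CDRS, CGI and QOL at early termination visits outside week 6, using existing raters, where consent has not been withdrawn (Section H stops data collection once it has). Section L models time as a trend, so an exit rating can enter at its actual time.
4. In the same amendment, align the wording of the PANSS withdrawal rule with the rating schedule. Item 3 does not by itself make that rule assessable between scheduled ratings.

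The cost is amendment wording, added items in the Section F early-termination list, marks in one column of Table 1, and at most about 10 sets of exit ratings at the planned discontinuation rate. The downside is a longer exit visit, and some ratings will not be obtained.

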Pregnancy Tests: A urine dip stick pregnancy tests will be administered to all women at screening. The pregnancy test can be repeated at any time during the study as per PI discretion. All subjects must test negative for pregnancy tests to be eligible for the study.

Urine Drug Tests: All subjects must undergo urine drug tests for a panel of substances at every study visit. The urine drug test will be completed prior to administering the timeline follow-back (TLFB).

The urine drug screen will include opioids, cocaine, methamphetamines, cannabinoids, barbiturates, benzodiazepines, methamphetamine, and phencyclidine.

Supportive Counseling: Qualified staff will provide supportive counseling to study subjects at weekly visits. Brief supportive counseling sessions about substance use will be provided as part of study visits. The content and structure is adapted

from the Individual Resiliency Training (IRT) manual that was originally developed for the RAISE (Research to identify, optimize and personalize early treatment for people affected by schizophrenia) study (Mueser et al., Psychiatric Services 2015; 66:680-690). Counseling will be provided to all subjects. Counseling is not manualized and no fidelity check is planned. Counseling will focus on:

1) substance abuse counseling to encourage a reduction in or abstinence from alcohol consumption;

2) Medication management counseling to encourage compliance with the treatment.

Efficacy Assessments

Timeline Follow-back (TLFB): Substance use will be recorded using the timeline follow-back method at every study visit. At screening visit, TLFB will assess substance use and dollar amount spent on substances for the past 30 days. All other visits will collect substance use data and dollar amount spent in the past week or for the period between the last visit and the current visit. The subject's drug screen results will be conveyed to the subject prior to administration of the TLFB. If the subject's self-report is at odds with the drug screen results, then the subject's report will not be challenged. All reported data from the subject and drug test results will be collected and used in exploratory analyses

Visual Analog Scale (VAS): The VAS will be used to assess craving for substance use as per the schedule of events and administered as per the schedule of events. The VAS is a horizontal line with a unipolar scale, anchored on the right side with

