If the subject is terminated from the study on what would be their week 6 visit, they will complete all the assessments that are required in a regular week 6 visit. If the subject is terminated from the study at any other point, only safety procedures will be performed (listed below).

- 1. Vital signs and anthropometric measures (weight)
- 2. Urine drug screen
- 3. TLFB
- 4. AE review
- 5. Safety labs (CMP, CBC, lipid panel)
- 6. ECG
- 7. CSSRS

G. TREATMENT OF SUBJECTS

Study Drug Dose and Administration

The study drug brexpiprazole (Rexulti) will be administered orally. Subjects will be randomly assigned to either switch to brexpiprazole or remain on the same antipsychotic medication (treatment as usual). Subjects randomized to brexiprazole treatment will be titrated as per section F (study intervention). Study participants randomized to brexpiprazole treatment will be titrated to 4mg/day or the highest tolerable dose as per the study MD's clinical judgement until the end of the study. Dose de-escalation due to tolerability will be allowed in the study. If subjects recover, the dose can be increased to the 4mg or the highest tolerable dose as per the MD's clinical judgement. Patients who are unable to tolerate a minimum dose of 1 mg will be withdrawn from the study

Study Drug

Commercially available brexpiprazole will be provided directly to all sites by Otsuka Pharmaceuticals. Study drug will be provided as 1mg and 2mg tablets. Subjects will take medications as dispensed by their site's Investigational drug pharmacy.

Storage and Drug Accountability

The study drug will be stored as per the drug insert. The sites are required to maintain current drug dispensation and accountability logs throughout the study. All unused supplies will be checked against the drug movement records during the study and/or at the end of the study.

Prohibited Medications

Currently on the following antipsychotics

- Aripiprazole
- Cariprazine

Currently on medications to treat substance use such as:

- Disulfiram,
- Naltrexone,
- Acamprosate,
- Methadone,
- Buprenorphine,
- Varenicline
- Bupropion

Special Consideration for Concomitant Medications with Brexpiprazole

Medications	Intervention
-------------	--------------

Strong CYP3A4 inhibitors	With concomitant use of brexpiprazole with a
	strong CYP3A4 inhibitor, reduce the brexpiprazole
Examples: itraconazole,	dosage and administration [see drug insert
clarithromycin, ketoconazole	dosage and administration (2.5)]

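### Withdrawal rules end follow-up as well as treatment, the two intolerance texts conflict, and an exit before week 6 leaves no scheduled post-baseline psychiatric or quality-of-life rating

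*Combined protocol and SAP*

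**What the plan says.** Section F, Withdrawal of Subjects, opens with an obligation: "The investigator must withdraw any subject from the study who requests to be withdrawn or fits the criteria below". Rule 1 on that list is "If subject meet any exclusion criteria after enrollment". Rule 3 covers any "increase in their PANSS total score greater than or equal to 20 compared to their baseline total score at any point during the study". Rule 2 (exclusionary laboratory values, after a repeat test) also ends in withdrawal.

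Rule 1 points back to the exclusion list in section D, which is introduced there as a check before randomization. The list includes psychiatric instability, with no definition; current aripiprazole or cariprazine; current medication for substance use; pregnancy; and previous exposure to brexpiprazole.

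Two places deal with intolerance. Section G, Study Drug Dose and Administration: "Patients who are unable to tolerate a minimum dose of 1 mg will be withdrawn from the study". Section F, Study intervention, says the drug is stopped but "the participant may continue to be followed on another treatment", and then has the subject finish the study on the previous antipsychotic.

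For early termination at week 6, section F asks for the full week 6 battery. Otherwise: "If the subject is terminated from the study at any other point, only safety procedures will be performed (listed below". That list holds vital signs and weight, urine drug screen, TLFB, adverse events, safety labs, ECG and C-SSRS. Note 5 to Table 1 agrees: "If ET falls on any other visit, follow ET protocol". Table 1 also marks VAS in the early-termination column, although the section F list leaves it out. Section E defers to the table: "The VAS will be used to assess craving for substance use as per the schedule of events".

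Section L plans an intent-to-treat mixed model over all 12 weeks, with baseline measures as covariates. It states no missing-data assumption and no sensitivity analysis.

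**The concern.** An intent-to-treat estimate over 12 weeks needs subjects to be observed after their treatment changes. Rule 1 instead ends observation when a subject starts another partial agonist or a substance-use medication, or is judged unstable. Such events may be related to outcome, and section F, Randomization, makes the assignment accessible to the site that judges them. If section G governs, the 1 mg rule removes subjects from the brexpiprazole arm only.

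The exit visit adds to the loss. Psychiatric symptoms and quality of life are secondary objectives with only two post-baseline time points, weeks 6 and 12. A subject withdrawn as unstable during the six-week switch would leave no scheduled post-baseline PANSS, even though the same subject leaving at week 6 would be fully rated. If baseline enters the model only as a covariate (section L does not say whether it is also an outcome row), that subject adds nothing to those analyses.

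**Working it through.** **Inputs.** 50 randomized, 20% discontinuation, 40 completers (section D). Weekly TLFB at weeks 1 to 12; PANSS, SANS, CDRS, CGI and QOL after baseline at weeks 6 and 12 only (Table 1, section E). Early-termination content from section F and Table 1, note 5.

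**The plan's own figure.** 40 / (1 − 0.20) = 50, which reproduces the target. Planned discontinuations: 50 × 0.20 = 10.

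**What each route out does.**

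| Route | When it can act | Effect on ratings |
|---|---|---|
| Rule 1 | Any week | None after baseline if before week 6 |
| Rule 3, scheduled PANSS | Week 6 or week 12 | At week 6, full battery taken and week 12 lost; at week 12, nothing lost |
| 1 mg rule, if section G governs | Any week, brexpiprazole arm only | None after baseline if before week 6 |
| 1 mg rule, if section F governs | No exit | None lost by rule |
| Any other exit | Any week | None after baseline if before week 6 |

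If an unscheduled PANSS triggered rule 3 before week 6, that PANSS would itself be a post-baseline rating, though the other scales would be missing.

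**Loss per subject**, for exit at week w (1 to 11) with the exit visit attended:
- Weekly TLFB records lost = 12 − w: week 1, 11; week 5, 7; week 6, 6; week 11, 1.
- Rating time points kept: 0 of 2 for weeks 1 to 5; 1 of 2 for weeks 6 to 11.

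**Range if all 10 planned discontinuations leave follow-up**, for whatever reason:
- No post-baseline rating: 0/50 (all exit at week 6 or later) to 10/50 = 20% (all exit in weeks 1 to 5).
- Rating time points lost, of 50 × 2 = 100: 10 × 1 = 10 to 10 × 2 = 20.
- TLFB records lost, of 50 × 12 = 600: 10 × 1 = 10 (1.7%) to 10 × 11 = 110 (18.3%). If all ten left before week 1 without an exit visit, 10 × 12 = 120 (20.0%).

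**One illustration inside the range.** Under an assumed constant exit hazard, h = −ln(0.80)/12 per week. Expected exits before week 6 are 50 × (1 − exp(−6h)) = 50 × (1 − √0.80) = 5.3.

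These counts vary only exit timing. The documents give no split by rule or arm.

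**The case against.** The strongest reply is that the loss is confined to secondary outcomes in a 50-subject proof-of-concept study. TLFB is weekly and kept at exit, VAS is marked at exit in Table 1, and data up to exit stay usable in a mixed model under missing at random. This stands and limits the weight of the point.

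A reader might infer that all three rules force subjects out and that each produces the total loss of ratings. The documents do not support that. Section F keeps intolerant subjects in follow-up, so the 1 mg sentence is one side of a contradiction. On scheduled ratings, rule 3 cuts follow-up only at week 6, after the full battery.

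A reader might also charge the 10 discontinuations to these rules. That figure covers every cause, and the range for unrated subjects includes zero.

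Read literally, rule 1 with the prior-exposure exclusion would remove every dosed brexpiprazole subject. That is not a sensible reading, and the criterion could still serve for undisclosed pre-study exposure. It shows only that rule 1 does not say which exclusions carry forward.

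Exit at a PANSS rise of 20 can be defended as participant protection. Protection may require a change of treatment, but it does not generally require observation to stop. Case-by-case waivers (section H) and the medical monitor (section J) can settle individual cases, but they do not define rule 1's scope. Central eligibility review comes before randomization and does not address later events.

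**Conclusion.** The point holds and should be fixed. Rules 1 and 3 are mandatory exits from the study, which works against the 12-week intent-to-treat aim. The two intolerance texts conflict for one arm. Independently of those rules, any exit before week 6 leaves no scheduled post-baseline psychiatric or quality-of-life rating. At the planned discontinuation this is 0 to 10 of 50 subjects, assuming that all 10 leave follow-up and that those leaving at week 6 or later have the week 6 ratings. A rule 3 exit at week 6 keeps those ratings but loses weeks 7 to 12, the whole period after the switchover.

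It would go too far to say that the primary analyses are undermined or that a bias in a known direction has been shown. The primary measures lose only the weeks after exit, and neither the number leaving under each rule nor the direction of any bias can be derived from the documents.

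**What to change.** 1. Add PANSS, SANS, CDRS, CGI and QOL to the early-termination visit, in both the section F list and Table 1, and add VAS to the section F list to match the table. The polynomial time model can use a rating at its actual date. With every exit visit attended, the 0 to 10 unrated subjects fall to 0.
2. Change the 1 mg sentence in section G to match section F. State that subjects in either arm who meet rule 1 or rule 3 stop or change treatment as clinically needed but remain in scheduled assessments to week 12, unless safety or withdrawn consent prevents it.
3. Limit rule 1 to a short list of exclusions meant to apply after randomization, leaving out on-study brexpiprazole exposure, and define psychiatric instability if it stays. Which exclusions to keep is the sponsor's choice.

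The same amendment could say whether rule 2 ends follow-up or only treatment, and align the pregnancy text: section F says such subjects may be terminated, section H says they will be withdrawn, and pregnancy is also an exclusion under rule 1.

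Cost: a protocol amendment using existing visits and scales, a longer exit visit, further visits for a few subjects, and some data collected under changed treatment. The gain reaches only subjects who attend and who exit after the amendment. Version 6.2 dates from January 2022 and first enrollment was expected in February 2018, so earlier exits cannot be recovered. Subjects who withdraw consent give no further data (section H).
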